In a pilot study where a technology enhanced training program for improving upper limb muscle strength in MS patients the TEMPA was used at baseline and 8 weeks later, and there was a trend towards statistical significance of improvement in function with TEMPA change of 20 to 40 seconds [14]. Since the 9HPT and TEMPA have been show to correlate and there are numerical values measured in both, we plan to emulate the Oratorio study and look at >15%, >20% and >25% [in better hand and in worse hand] change from baseline with increases in time implying clinical progression and stability or decrease in time implying stability or improvement in function.

The Jamar dynamometer is validated tool often used by occupational therapist to measure grip strength [15]. Grip strength is an important part of daily living tasks and can give clinicians insight into patient restrictions and clinical changes.

The Upper Extremity Functional Index (UEFI) is a self-report questionnaire that has been found reliable, valid and sensitive as a patient- reported outcome measure tool for quantifying UE function rated on a 5-point Likert scale This 20item measure is recommended in research and clinical setting due to its unidimensionality: it measures only UE function [16,17]. Scores range from 0 to 60 with lower scores indicating more functional difficulty. It has been used in several studies in patients with musculoskeletal upper extremity problems, to include patients with MS, and UEFI scores correlated with mean 9-HPT scores. [18] We anticipate that patients in our study will have perceived stabilization of their upper extremity function and plan to use the UEFI to measure this by means of its validated 9 points of change from baseline for minimal detectable change in function.

The Symbol Digit Modalities Test (SDMT) is a validated measure used to assess mental processing speed in MS clinical trials and has an oral response version. There is evidence that cognitive measures may correlate with upper extremity function. This can possibly be explained by a cerebral relationship between motor function and cognition [19]. As a secondary measure we will collect SDMTs at each visit to explore correlations with upper extremity function, as well as QoL measures.

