3.3.2 Secondary Outcome Measures

No significant change in UEFI, or 9HPT from baseline to 24 months. Exploratory measures: correlations between change in TEMPA/UEFI/9HPT scores and FSS, MUSIQOL and SDMT values from baseline through 24months after treatment initiation with Ocrevus[™].

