4.1.3 Exclusion Criteria

Candidates will be excluded from study entry if any of the following exclusion criteria exist at the time of study entry:

- Severe weakness in bilateral upper limbs causing complete loss of function
- History of severe allergic or anaphylactic reactions or known drug hypersensitivity
- Female subjects considering becoming pregnant while in the study
- Female subjects who are currently pregnant or breast-feeding
- Unwillingness or inability to comply with the requirements of the protocol including the presence of any conditional (physical, mental or social) that is likely to affect the subject's ability to comply with the protocol.
- Active HBV infections
- Prior treatment with Ocrevus™
- Severe tremor/ataxia of the UE as defined by an EDSS with Cerebellar Functional System score of 3 or more due to upper extremity score (moderate tremor or clumsy movements interfere with function in all spheres)

- Severe spasticity of the UE as defined by EDSS, Pyramidal Functional System score- Upper Limb spasticity subscore of 3 or more (severely increased muscle tone that is extremely difficult to overcome and full range of motion is not possible)
- Cognitive impairment that may interfere with the conduct of the necessary testing (determined by the investigator)
- Any other reason that, in opinion of the Investigator and/or the Sponsor, the subject is determined to be unsuitable for enrollment in this study

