4.9.3 Efficacy Analysis

a. Primary Endpoint

1. TEMPA scores after 24 months of Ocrevus[™] treatment. Paired sample t-test to compare the 24 month measurements to the baseline measurements.

Mean within-patient changes from baseline through 24 months (TEMPA). Oneway repeated measures ANCOVA for TEMPA scores from baseline, 6 months, 12 months, 18 months, 24 months which will account for baseline characteristics (baseline disability level). A soft stratification will be applied so that recruitment will aim to include a spread of types of patients, those below overall EDSS of 6.0 and those above 6.0. If more than 2/3 of total enrollment is in one of the categories, the study team will reestablish efforts to recruit for the other cohort.

If data does not have normal distribution, then other non-parametric analysis will be employed (such as sign test for TEMPA functional score).

The threshold to determine a significant clinical change will be >20% from baseline value. This clinically significant difference is estimated based on data from the Oratorio trials that showed progression among both groups (placebo and OcrevusTM) but to a lesser extent in the OcrevusTM arm with an established clinically significant threshold of 20% (data will be requested from sponsor for use to review 9HPT results for the abnormal function at baseline group of patients). Measures will be collected and analyzed as units of time (seconds) and as functional scores on an ordinal scale that range from 0 to -3 (0 indicating

no signs of dysfunction).Ad hoc analysis may occur that includes evaluation of patients with significant clinical changes versus those that did not have significant clinical change based on any of the subscales within the TEMPA or physical exam. We will review >15%, >20% and >25% [in better hand and in worse hand] change from baseline with increases in time implying clinical progression and stability or decrease in time implying stability or improvement in function

b. Secondary Endpoints

Pearson correlation coefficients will be calculated to evaluate correlations between UE function (measured by TEMPA and 9HPT) primarily at baseline but also at each time point over the 24-month time period to compare patient responses on the UEFI, FSS, and MUSIQOL. Correlations with the primary endpoint scores and the SDMT will also be analyzed for any indication of new cognitive impairment that may interfere with the interpretation of the results.

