APPENDIX A Schedule of Assessments

	Screening/ BL ^{1,2}	M3	M6 ³	M9	M12 ³	M15	M18 ³	M21	M24 ³
Informed Consent	Х								
Review of Medical History	Х								
Review of inclusion/exclusion	Х								
Concomitant Medications	Х	Х	Х	Х	Х	Х	Х	Х	Х
Demographics	Х								
Patient Questionnnaires (UEFI, SDMT, FSS, MUSIQOL)	X	Х	Х	Х	Х	Х	Х	Х	Х
Physical Exam (and EDSS)	Х		Х		Х		Х		Х
Vital Signs	Х	X ⁴	Х	X4	Х	X4	Х	X4	Х
Interval History	Х	Х	Х	Х	Х	Х	Х	Х	Х
Review AEs	Х	Х	Х	Х	Х	Х	Х	Х	Х
Measurement of UE function (TEMPA, 9HPT, Jamar dynamometer)	Х		X		X		X		Х
Relapse Assessment ⁵	Х	Х	X	Х	Х	Х	X	Х	Х

1. The baseline visit will occur within 4 weeks of the screening visit.

2. Acceptable windows for all visits are +/- 14 days. In rare cases where the first infusion is greater than 2 months from the baseline visit, the month 3 visit and subsequent visits will be calculated based on the initial infusion date.

3. Semiannual visits will occur prior to the next scheduled Ocrevus™ infusion

4. Vitals signs will be collected for subjects who conduct the quarterly visit at clinic. Vital signs will not be collected at quarterly visits conducted via phone.

5. If relapse is suspected, this will be captured as an AE and treated at the discretion of the investigator. Documentation will include any suspicion for PML

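### The TEMPA-SDMT correlation is not a measure of SDMT decline, and the plan specifies no SDMT change-from-baseline analysis or decline criterion to detect new cognitive impairment

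*Combined protocol and SAP*

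**What the plan says.** Section 4.9.3b gives the SDMT one interpretive task: "Correlations with the primary endpoint scores and the SDMT will also be analyzed for any indication of new cognitive impairment". The target is "new cognitive impairment that may interfere with the interpretation of the results". The only statistic named in that paragraph comes in the sentence before: "Pearson correlation coefficients will be calculated to evaluate correlations between UE function (measured by TEMPA and 9HPT) primarily at baseline but also at each time" (that sentence then runs on to span the whole of follow-up).

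Three other places bear on the point:

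- Section 3.2 describes the SDMT only through correlations: "As a secondary measure we will collect SDMTs at each visit to explore correlations with upper extremity function, as well as QoL measures".
- Section 3.3.2 lists as exploratory "correlations between change in TEMPA/UEFI/9HPT scores and FSS, MUSIQOL and SDMT values from baseline through 24months". It does not say whether the SDMT enters as a level or as a change.
- Section 4.1.3 excludes at entry "Cognitive impairment that may interfere with the conduct of the necessary testing (determined by the investigator"), with no SDMT cut-off. This does not address decline after entry.

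Appendix A schedules the SDMT at baseline and every three months to month 24, within the row "Patient Questionnnaires (UEFI, SDMT, FSS, MUSIQOL"). TEMPA is measured at baseline and months 6, 12, 18 and 24. Nowhere do the documents specify a summary of SDMT change from baseline, a threshold for new impairment, a count of patients who decline, or how their TEMPA results should be read.

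**The concern.** New impairment is a change within a patient over time. A correlation at a visit describes how patients rank against each other at that visit. It answers whether slower TEMPA goes with lower SDMT, not whether SDMT has fallen.

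The check protects the reading of the primary outcome. TEMPA is a set of timed daily-living tasks, and the authors recognise that cognitive decline could interfere with interpreting it. With one arm and about 30 patients, no control group can help separate slowing of the arm from slowing of thought. If the chosen statistic can stay still while cognition worsens, a reassuring correlation could be reported when the concern it was meant to exclude is present.

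**Working it through.** The plan states no figure for this check, and section 4.9.6 says that the sample size was not calculated, so there is nothing to reproduce. The only input from the documents is n=30 (section 4.9.6). They give no SDMT mean, SD or change threshold, so every distributional value below is an assumption.

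**1. Uniform or proportional fall (algebra, no assumptions).** For TEMPA score T and SDMT score S, corr(T, a + bS) = corr(T, S) whenever b > 0. A fall of 10 points for everyone is a = -10, b = 1. A 20% fall for everyone is a = 0, b = 0.8. In one simulated sample of 30, r was -0.439 before the fall, -0.439 after the 10-point fall and -0.439 after the 20% fall.

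**2. A few decliners.** Assumed: true r of -0.4 between TEMPA time and SDMT, SDMT SD of 8 to 15, and 6 of 30 patients falling 15 points with no other change. The mean shift in r depends on who declines:

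| Who declines | Shift in r, SDMT SD 8 | Shift in r, SDMT SD 15 |
|---|---|---|
| 6 at random with respect to TEMPA | +0.08 | +0.03 |
| 6 slowest on TEMPA | -0.26 | -0.18 |
| 6 fastest on TEMPA | +0.52 | +0.28 |

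The sampling SD of r at n=30 is about 0.16. Random decliners therefore move r by at most half of one SD (0.08/0.16 = 0.5). Decliners at one end of the TEMPA range move it by more than one SD, strengthening the correlation in one case and weakening or reversing it in the other.

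**3. Precision of r.** With 28 degrees of freedom, |r| must reach 0.36 for two-sided p<0.05. The Fisher z interval around |r| = 0.4 is tanh(0.424 ± 1.96/√27), or 0.05 to 0.66.

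**4. The direct alternative.** The 95% CI half-width for mean SDMT change is t(0.975, 29) × SD/√30:

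- assumed SD of change 5: 2.045 × 5/5.477 = 1.9 points
- assumed SD of change 8: 2.045 × 8/5.477 = 3.0 points

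Power of a paired t-test (two-sided 0.05, n=30) for a mean fall of 5 points is above 0.99 at SD 5 and 0.91 at SD 8. For a fall of 3 points it is 0.89 and 0.51.

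**5. The two side by side.** A separate simulation added visit-to-visit noise (assumed 5 SDMT points and 20 s on TEMPA; SDMT SD 12, r -0.4). A uniform 10-point fall was detected by the paired SDMT test in 100% of trials and by the change in r in about 5%, the false-positive rate. With a 15-point fall in a random 30% of patients, the figures were 81% and 17%. The rates for r flatter it, because they use a reference range from simulated trials without decline, which the protocol does not plan.

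**The case against.** Three objections have force.

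**The correlation is not blind to every decline.** A reader might infer that r never moves when SDMT falls, or that the check is bound to report nothing. The documents and the arithmetic do not support that. Invariance is exact only for a uniform or proportional fall, and the smaller-than-noise result holds only if decliners are unrelated to TEMPA level. Where decline follows TEMPA level, r can move substantially. What remains is that a moved r is ambiguous. It may strengthen or weaken, TEMPA change or noise can also move it, and it identifies neither the patients nor the size of the fall.

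**The plan may intend a correlation of changes.** The primary outcome is defined against baseline, and section 3.3.2 correlates change in TEMPA with SDMT values. If SDMT also entered as change, the result would bear on whether the two move together, which is part of the stated purpose. In a simulation where 6 of 30 patients lost 15 SDMT points and slowed by 40 s (assumed SDs of change of 5 to 8 points and 20 to 30 s), that correlation was significant in 34% to 84% of trials. So it carries information. It still would not show that SDMT fell, since r ignores the mean change, and the text leaves the form of the SDMT variable open.

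**This is a small pilot and the correlations are exploratory.** The primary analysis does not use the SDMT, and change could be tabulated later from data already held. That limits the weight of the point. It does not make the named statistic suited to its named task, and a decline criterion chosen after seeing the data is less convincing than one set beforehand.

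**Conclusion.** The point holds in this form: the correlation that section 4.9.3b assigns to detecting new cognitive impairment does not measure SDMT decline, and the plan has no analysis that does. The invariance to a uniform or proportional fall is algebra and needs no assumption. The shift of 0.03 to 0.08 against an SD of about 0.16 rests on n=30, true r of -0.4, SDMT SD of 8 to 15, and 6 random patients falling 15 points. None of these except n is in the documents. When decline is related to TEMPA level, the shift is larger but can go either way (-0.26 to +0.52 over the same range).

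It would go too far to infer that the primary TEMPA analysis is invalid. That analysis stands apart from the SDMT. What is weakened is the planned safeguard on its interpretation.

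**What to change.** In section 4.9.3b:

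1. Make within-patient SDMT change from baseline at months 6, 12, 18 and 24 the check for new cognitive impairment. Report the mean with its 95% CI (half-width about 1.9 to 3.0 points at month 24 with 30 patients, if the SD of change is 5 to 8; wider with fewer). Also report the number of patients meeting a decline criterion that is fixed and justified in advance. These are the visits at which TEMPA is also measured.
2. Keep the TEMPA-SDMT correlations as descriptive, and state in section 3.3.2 whether the SDMT enters as level or change.
3. Leave the primary analysis unchanged. Beside it, as a supportive sensitivity analysis only, report TEMPA with and without decliners, or with SDMT change as a covariate. State the caution that this conditions on a post-baseline variable: removing or adjusting for patients who progressed may favour apparent stability.

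The cost is a change of wording, one extra table and one sensitivity analysis. No new data are needed, because the SDMT is already scheduled at every visit.

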4.9.4 Safety Analysis

No safety analysis will occur as these patients will be receiving commercial Ocrevus. A summary of adverse events will be constructed using descriptive statistics.

4.9.5 Missing Data

Study staff will work to ensure missing data is minimized. If there are less than two percent of time points missing, then during analysis, last value carry forward imputation will be used. If greater than two percent missing, multiple point imputation measures will be used.

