The TEMPA scale is composed of nine standardized tasks which represents activities of daily living. Four items are unilateral (pick up and move a jar; pick up a pitcher and pour water into a glass; handle coins; pick up and move small objects) and five bilateral tasks (open a jar and take a spoonful of coffee; unlock a lock and open a pill container; write on an envelope and stick on a stamp; shuffle and deal playing cards; put a scarf around one 's neck). The outcome parameters used in this study are speed of execution (seconds) and the functional rating. The functional rating refers to the participant's independence in each task measured on a four-level scale: (0) successfully completed without hesitation or difficulty; (-1) completed, but with some difficulty; (-2) partially executed or some steps were performed with significant difficulty; and (-3) not completed, even if any degree of assistance was offered. A total score will be determined by adding the scores obtained for both the unilateral and bilateral tasks. Individual analysis of the unilateral and bilateral scores will be conducted to evaluate for functional improvement in the affected UE. Scores typically range from 0 to -50, with higher scores representing better performance. [12] The UE function will be measured by a consistent rater that is trained and qualified (must be a MD or equivalent).

The 9HPT is an objective measure of manual dexterity, which is incorporated into the MSFC, is a widely used measure across most clinical trials in multiple sclerosis populations. The time to completion is measured twice on both the dominant and non-dominant hand. For this study purpose will also record the "better" and "worse" limb so that the data can be cautiously compared to prior studies completed in multiple sclerosis patients. The task of the 9HPT is for the patient to pick up each individual peg, one at a time, and place it in the board (that has the same number of peg holes for each peg). Once all the pegs are placed in the peg holes the patient then removes each peg, again one at a time, placing them back into the peg bowl from which they were originally located. Although this measure has been used in several multiple sclerosis trials due to its ease of administration, there are many other factors of upper extremity function that are not being assessed that can be captured by the TEMPA.

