3.3.1 Primary Outcome Measure

No significant change in UE function over 24 months after initiation of Ocrevus™ measured objectively by measure of time to completion (seconds) and functional

scores on TEMPA (0 to -3). The hypothesis is that there is (stabilization) no significant change (within 20%) of TEMPA score from baseline to 24 months

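### TEMPA time is part of the primary outcome, but no time is defined for a task that can no longer be completed, and section 4.9.5 would treat a blank time from inability like a missed visit

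*Combined protocol and SAP*

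**What the plan says.** Section 3.3.1 defines the primary outcome by TEMPA time and TEMPA functional score together: "The hypothesis is that there is (stabilization) no significant change (within 20%) of TEMPA score from baseline to 24 months". Section 4.9.3 confirms that both are analysed: "Measures will be collected and analyzed as units of time (seconds) and as functional scores on an ordinal scale". It sets more than 20% from baseline as the threshold for clinical change and also reviews 15%, 20% and 25% in the better and worse hand, with "increases in time implying clinical progression and stability or decrease in time implying stability or improvement in function". Section 4.9.6 states the aim as the percentage of patients who stay within 20% of baseline.

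For a task that is not completed, section 3.3 gives a rating only. The two worst grades, minus 2 and minus 3, read "2) partially executed or some steps were performed with significant difficulty; and (-3) not completed, even if any degree of assistance was offered". No visible section attaches a time, a cap, a rank or an exclusion rule to such a task.

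On missing data, section 4.9.5 says that, with under two percent of time points missing, "last value carry forward imputation will be used. If greater than two percent missing, multiple point imputation measures will be used". The imputation model is not described. The percentage is the only criterion.

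**The concern.** Losing the ability to do a task is the clearest form of the worsening this study looks for, and it is also the event that leaves no time to record. If the blank is handled by section 4.9.5, the worsening is replaced by a value from a test that was completed. The error then runs toward the study's own hypothesis, and with no comparator arm nothing offsets it.

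The rating does not fully identify these cases. Minus 3 means not completed, but minus 2 also covers partial execution, so a reader of the data could not always tell which times should be absent. Section 4.1.2 requires the patient to be able to perform the tests with at least one limb, while section 4.9.3 analyses both hands. A hand time may therefore be absent already at baseline.

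**Working it through.** The plan has no figure to reproduce: section 4.9.6 says the 30 patients are not a calculated sample size, and no failure rate is given. The steps below show direction and possible size.

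**Inputs from the documents.** 30 patients (4.9.6); nine tasks, of which four are unilateral (3.3); 20% threshold (4.9.3, 4.9.6); TEMPA times of 100 to 400 seconds in an MS validity study and a 20 to 40 second change in a pilot study (3.2).

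**Assumed inputs.** The time of an uncompleted task is left blank; k patients lose a task or hand by month 24; 70% to 90% of the other patients are stable; tasks take equal time.

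**1. Carried forward, or imputed close to completed times.** The patient is called stable unless already more than 20% slower at the value used. Overstatement is at most k/30:

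| k | 0 | 1 | 2 | 3 | 5 |
|---|---|---|---|---|---|
| points, at most | 0 | 3.3 | 6.7 | 10.0 | 16.7 |

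**2. Patient dropped.** With failures counted as not stable, the share is p(30 − k)/30; with them dropped it is p. The difference is p·k/30:

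| k | 0 | 1 | 2 | 3 | 5 |
|---|---|---|---|---|---|
| p = 0.7 | 0 | 2.3 | 4.7 | 7.0 | 11.7 |
| p = 0.9 | 0 | 3.0 | 6.0 | 9.0 | 15.0 |

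**3. Remaining tasks summed.** If the lost task is a share s of the baseline total and the rest are unchanged, the total falls by s. The rest must slow by 1.2/(1 − s) − 1 before the total passes +20%.

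- One of nine tasks: s = 1/9, a fall of 11.1%. Slowing allowed is 1.2/(8/9) − 1 = 35%. The fall lies within 20%, so the patient reads as stable.
- One of four unilateral tasks: s = 1/4, a fall of 25%. Slowing allowed is 1.2/0.75 − 1 = 60%. The fall exceeds 20%, so the patient reads as improved.

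On totals of 100 to 400 seconds, one ninth is 11 to 44 seconds, similar in size to the 20 to 40 seconds that section 3.2 cites as a trend toward improvement.

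**The case against.** The strongest reply is that section 4.9.5 may not be triggered. It speaks of missing time points, and a patient who attends and fails one task still supplies other times and a rating. No passage says that the rater leaves the time blank. TEMPA is a published instrument, and its instructions, like the content of Appendix F for the 9HPT, may set a time limit that is not visible here. This stands as a limit on the point. It does not close the gap, because the plan neither states nor refers to such a limit.

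Failures may also be uncommon. Entry weakness is defined as grade 4/5 (4.1.2), severe tremor, ataxia and spasticity are excluded (4.1.3), and section 3.2 shows that very slow patients were still timed. That is why the size is left open.

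The functional score does record inability, and the sign test that section 4.9.3 mentions ("then other non-parametric analysis will be employed (such as sign test for TEMPA functional score") would count any worsening of it. This stands too. However, the plan does not say how time and function combine into one judgement of stability, so a failure seen in one need not correct the other.

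Three stronger readings are tempting and not supported.

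- A reader might infer that every route raises the percentage stable. The second case in step 3 reads as improvement, which section 3.3 lists separately from stability.
- A reader might infer that the functional total would miss a single lost task under the 20% rule. Section 3.3 says "A total score will be determined by adding the scores obtained for both the unilateral and bilateral tasks" and gives a range to −50, but nine ratings reach only −27, and rating the four unilateral tasks in each hand (8 + 5 = 13 ratings) reaches −39. The make-up of the total is too unclear for such a cut-off.
- A reader might infer which rule a single failure would trigger. Inability from month 12 on is three absent values: 3/150 = 2.0% with baseline counted, 3/120 = 2.5% without. The plan does not fix the denominator, and other missing data would change the result.

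**Conclusion.** The point holds and should be fixed, with medium confidence. The primary time measure has no stated value for a task the patient can no longer do, and the missing-data rule does not separate inability from a missed visit. If such times are left blank, carrying forward, imputing from observed times and dropping the patient each tend to overstate the percentage stable, by up to 3.3 points per affected patient. Summing the remaining tasks can make a loss read as stability or improvement.

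The total effect is unknown. It is near zero if failures are rare and several points if two or three of 30 patients are affected. The documents do not support a claim that the result will be biased by any particular amount.

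**What to change.** Amend section 4.9.5 as follows.

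- **(a)** A TEMPA time or 9HPT hand time obtained at baseline and later unobtainable because of functional inability is an observed failure, not missing data. It is neither carried forward nor imputed as missing. No total is formed from fewer tasks than at baseline, and the patient counts as not stable on that time measure. If the test instructions set a time limit, state it and say how a capped time enters the 20% rule.
- **(b)** Carrying forward or imputation applies only to absence unrelated to function. Record completed yes/no for each task and a reason for each missing time.
- **(c)** Hands or tasks that could not be completed at baseline are reported separately, outside the denominator for time stability.
- **(d)** Keep the t-test and ANCOVA on seconds and show the number of failures beside each. Because a failure has no value in those tests, add a sensitivity analysis that keeps the patient by setting the failed task to the longest observed (or capped) time. If a non-parametric test is used on time, a failure counts as worsening in a sign test or takes the worst rank in a rank test.

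The cost is wording in 4.9.5, a line in 4.9.3 and two data fields, with no added visits or patients. The downsides are real. The percentage stable may fall by up to 3.3 points per failure. One failed task may overstate progression, so show the percentage stable both ways: with failure counted as not stable, and with the substituted time judged by the 20% rule. The substituted time is arbitrary.
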